9 IDENTIFICATION AND RECRUITMENT OF GP PRACTICES

9.1 Identification of GP practices

Internal Pilot Phase: Twelve practices (average approximately 10,000 patients per site- using a 'hub and spoke' research practices approach if required in some sites) will be involved in this phase. Two of these practices will be those in which GP members of the research team are based. The remaining ten practices will be randomly selected from the full list of practices at each site. The practices will be matched according to high vs low deprivation and size (large/medium/small) before cluster randomisation. The aim will be to recruit a wide spectrum of communities.

Main study: Approximately 45 practices will be involved in the main trial, including the twelve from the pilot trial.

9.2 Recruitment of GP practices

The PI or other member of the research team at each site will send an invitation letter to the research GP lead and practice manager at each practice identified as being potentially suitable for the study. Invitation letters will include an information sheet about the study. Invitation letters will be followed up by a telephone call from a member of the research team to ascertain interest and if appropriate arrange a meeting at the practice to discuss the study in more detail. Local research teams will work closely with the Clinical Research Network (CRN) to recruit suitable practices.

10 PARTICIPANT SELECTION AND RECRUITMENT

Patients with a history of depression (with or without anxiety) within the last 12 months and who are worried about personal debt will be recruited through participating GP practices at the study sites. Depression at screening will be classified according to the Beck Depression Inventory (BDI) score where 14-19 = mild depression, 20-28 = moderate depression, >28 = severe depression.

10.1 Inclusion Criteria

- Age ≥ 18
- Scoring ≥ 14 on the BDI
- Self-identifying as having worries about debt

10.2 Exclusion Criteria

- Actively suicidal or psychotic and/or severely depressed and unresponsive to treatment
- Unlikely to comply with the intervention or follow-up e.g. experiencing severe problems with addiction to alcohol or illicit drugs
- Unable or unwilling to give written informed consent to participate in study
- Currently participating in another research study including follow-up data collection phase
- Has received CAB debt advice in the past 12 months

10.3 Identification and recruitment of participants

Participants will be identified and recruited via GP practices by two methods:

General Practice (GP) database searches

Supported by members of the local PI's research team and clinical research network staff, GP practices will identify adults potentially having current depression or depression related treatment in the last 12 months from practice database searches (use of antidepressants, diagnostic codes, QOF depression score codes). GPs may screen generated patient lists should they wish to do so to exclude any patients they deem it would be inappropriate to approach. Practices will then send out standard letters to potentially eligible patients, informing them of the study and inviting them to contact the research team. Practices will be offered Docmail service as an alternative to practice staff conducting mail out activities. Practices will be able to choose whether to use Docmail service or not.

Accompanying the trial invitation letter will be a flyer which provides a 'quick read', a participant information sheet, an expression of interest form and a Freepost envelope. The invitation letter will

ask patients to complete and return the expression of interest form in the Freepost envelope provided if they are interested in taking part in the study. On receipt of the completed form the local research assistant (RA) or other research team member will contact the individual by telephone, explain the study in detail, answer any questions the individual may have and assess initial eligibility (that they have worries about debt that they are personally responsible for, that they are not currently taking part in other research, that they have not had any advice from CAB in the past 12 months). If the person is still interested in taking part in the study and eligible at this point, the researcher will arrange a date and time to meet with the patient to complete the final stage of eligibility – Beck Depression Inventory. Should there be no response to the initial telephone call, the researcher will make reasonable further attempts to contact the individual, after which it will be assumed that the person is no longer interested in taking part.

Waiting room recruitment

Publicity posters will be displayed in the waiting rooms of participating GP practices and flyers outlining the study will be placed around the waiting room. Posters and flyers will be REC-approved and updated from time to time, as required. Flyers will include the contact details (telephone number/e-mail address) of the RA at the relevant site. Expression of interest forms and Freepost envelopes will also be freely available at the practice so that patients can choose to return an expression of interest form to the local research team (as described above), or telephone the research team for more information.

Clinical Research Network (CRN) researchers and the RA may also highlight the study to patients in the waiting room by handing out flyers and asking people to approach them or a member of the practice reception staff if they would like to discuss the study in more detail. Members of the GP practice staff may also highlight the study to patients by handing out flyers (with attached expression of interest forms) to patients when they are attending the practice. Where the researcher is available in the practice, patients registering their interest in the study will be taken into a side room to discuss the study in more detail and be handed the participant information sheet to read. The researcher will explain that patients will be screened for eligibility at their baseline data collection and consent visit. Patients interested in taking part in the study after discussion and reading of the participant information leaflet will be asked to complete an expression of interest form and the researcher will arrange a date and time to meet with the patient to complete the baseline assessment. In the event that a CRN researcher is present at the GP practice rather than the study RA the CRN researcher will explain that the completed expression of interest form will be passed to the study RA who will contact the patient to arrange a baseline assessment visit.

Some potential participants may opt to check eligibility there and then in the GP practice, so will complete the consent process at that point and complete their baseline BDI. Where people complete the BDI in their GP practice, they will be advised that the score will be carried over to the baseline assessment visit and will be the data used for the study, unless that visit takes place more than two weeks later, in which case, the participant would be asked to complete the BDI again at the baseline visit to determine eligibility and for use as baseline data for the study. Patients who are not eligible to take part (i.e. scoring <14) will be advised as to why they are not eligible to take part, thanked for their time and willingness to participate and given the same study-specific debt advice leaflet and the Royal College of Psychiatrists (RCPsych) 'Debt and mental health' advice leaflet as those given to people participating in the study. Ineligible patients will have no further involvement in the study.

Some patients may choose to take the expression of interest form away with them and return it completed to the research team in a Freepost envelope at a later date rather than completing

paperwork or booking an appointment at that time. On receipt of a completed form the local research assistant will contact the individual by telephone to book a baseline appointment.

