11 RANDOMISATION

In the internal pilot trial, relevant GP practice demographic information will be sent to CTU/study statistician by CRN in England, this activity will be supported by ABMU Health Board in Wales. Four practices (matched on their size and deprivation index score) in each of the three trial localities will be randomised to intervention or control arms and cluster (practice) or individual (patient) level allocation such that six practices are randomised to cluster allocation and six practices to individual allocation. To achieve total population research practice sites may be combined using a hub and spoke approach where available. The randomisation sequences and matching will be computer generated undertaken by an independent statistician working with the CTU. The CTU programming team will run checks before and during the trial to verify the integrity of the randomisation system.

Should the internal pilot show contamination to be a problem, for the main trial, the remaining practices will be randomised to intervention or control stratified by size and the deprivation (higher vs lower) of the populations they serve. If contamination is not found to be a problem, participants would be individually randomised to intervention or control.

Additional practices for the main trial will be identified and recruited once a decision has been made at the end of the internal pilot whether randomisation will be individual or cluster.

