11.2 Cluster level randomisation procedure

During the internal pilot trial (and main trial if cluster randomisation continues), participants recruited at cluster randomised practices will be registered on the main trial database as soon as possible following written consent. A member of the research team (usually the RA) will access the

password-protected registration website and enter the required participant details, including GP practice and identified staff member e-mail address, in order to register the participant on the trial. This process will trigger an automatic email to the relevant member of the practice staff confirming the participant's consent and registration. The member of staff will forward the e-mail to the appropriate study GP. Both the member of staff and the study GP will access the web-based database to obtain the participant's personal details. For trial management purposes, automatic confirmatory emails (not including allocation) will also be sent to relevant team members e.g. Chief Investigator, trial manager, local PI as appropriate.

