14 TRAINING

The lead study GP in each participating practice and his/her nominated deputy will be trained before starting recruitment in the trial design, assessment protocol and NICE guided 'treatment as usual' pathways. The local manager will visit to support recruitment, check fidelity to protocol and answer queries. This is likely to be monthly initially and then every 6-8 weeks once the study is established.

Researchers conducting qualitative interviews (see section 16.2) will receive training from experienced CAB staff who work in the field of debt and mental health and from service user advisors. Specific training and supervision will be provided by senior academics to ensure researchers develop the relevant skills to conduct interviews effectively: both from an ethical and scientific standpoint. Participants may be particularly concerned about issues such as confidentiality and how their data are reported and handled and assurances will be given at the interview, alongside the information sheet and the consent process. All aspects of the interviews and topic guides will reflect these sensitivities.

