We propose to compare our two recruitment methods. 1) Supported by ourselves, the networks and service support cost funding, practices will identify adults potentially having current depression or treatment for depression in the last 12 months from GP database searches (use of antidepressants, diagnostic codes, QOF depression score codes), and send out letters informing them of the study and inviting them to contact the research team. 2) We will also recruit direct from general practice waiting rooms supplemented by publicity material at reception and waiting areas. Our experience of consultation-based recruitment is that it is relatively inefficient in primary care mental health trials^{viii}. At the end of the internal pilot trial we will compare key characteristics (demographics, debt and depression severity) of those recruited through mailshots versus direct contact, and within cluster versus individually randomised sites, to look for evidence of imbalances between the approaches that might introduce significant bias. We will also consider the relative resources required per recruit in terms of recruitment rate, staff resources associated with them, participant feedback on acceptability, refusal rates and practice teams' attitudes to mailshots v waiting room recruitment. This will supplement active recruitment monitoring throughout the trial to identify barriers to, and solutions for facilitating, recruitment. In the absence of clear evidence that individual factors such as sex, age, severity of debt or depression will have a substantially greater impact on outcome than other variations we do not intend to stratify our recruitment.

Acceptability of intervention and trial

Data will be used from qualitative interviews about participants' experiences of the trial and intervention and which with data on appointment attendance rates will be used to assess acceptability in the internal pilot trial. We intend to monitor attendance rates overall at assessment and advice sessions, and relative rates according to deprivation.

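### In cluster-allocated practices nothing prevents GPs from screening the invitation list after the practice knows its arm, and the planned recruitment check shows arm-related selection only in part

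*Protocol*

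**What the plan says.** **Allocation of practices.** Protocol section 11 says of the pilot that "Four practices (matched on their size and deprivation index score) in each of the three trial localities will be randomised to intervention or control arms". The same section adds that "six practices are randomised to cluster allocation and six practices to individual allocation". If contamination is found, in the main trial "the remaining practices will be randomised to intervention or control stratified by size and the deprivation".

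**Order of events.** In individually randomised practices the allocation is generated after consent (11.1). In cluster practices nothing is randomised at that point. Section 11.2 says that "participants recruited at cluster randomised practices will be registered on the main trial database as soon as possible following written consent", and the resulting e-mail to the practice confirms consent and registration only.

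**Who influences the invitation.** For the database route, section 10.3 says "GPs may screen generated patient lists should they wish to do so to exclude any patients they deem it would be inappropriate to approach". It gives no criteria, no exclusion log and no timing relative to the practice's allocation. For the waiting-room route, "Members of the GP practice staff may also highlight the study to patients by handing out flyers".

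**Who knows what.** Section 11.3 withholds allocation from the assessing researchers and from no one else. Section 14 says of the lead GP in each practice that this GP and "his/her nominated deputy will be trained before starting recruitment in the trial design".

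**The planned check.** At the end of the pilot, section 22.2 compares demographics, debt and depression severity between mailshot and direct-contact recruits and "within cluster versus individually randomised sites, to look for evidence of imbalances between the approaches that might introduce significant bias". Section 24 then allows a recruitment method to be dropped if it distorts the sample.

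**The concern.** Individual randomisation after consent protects the comparison whatever the GP did to the list, because the same selected patients are then split between the arms. Cluster allocation lacks that protection. If intervention practices tend to keep patients whom they expect to take up debt advice, and control practices remove patients for whom they feel they have little to offer, the two arms hold different kinds of patient before treatment begins. Randomising the practices does not correct this. Adjustment for the baseline score removes only the part of the difference that baseline BDI carries, not the part due to motivation, type of debt or response to earlier treatment.

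Pilot data enter the final analysis (sections 7 and 21.2), so some cluster-allocated patients contribute whichever way the main trial goes. If it switches to clusters, most of the sample does.

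**Working it through.** **1. Reproducing the plan's own figures (section 21.1).** Difference 3.5, SD 9, two-sided 5%, 90% power:

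- n per arm = 2 × (9/3.5)² × (1.960 + 1.282)² ≈ 139, against 135 stated. Power at 135 per arm is 89.2%.
- Design effect = 1 + (10 − 1) × 0.05 = 1.45, as stated.

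These inputs can therefore be used for scale.

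**2. How many patients are exposed.** The pilot takes 120 patients at about 10 per practice (section 23), half of the practices being cluster-allocated, so about 60 patients. An even split gives about 30 per arm. The even split is an assumption, but it agrees with the 30 individually randomised controls named in section 8.2.

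| Main trial | Total per arm (21.1) | Cluster-allocated per arm | Share |
|---|---|---|---|
| Individual | 195 | 30 | 30/195 = 15% |
| Cluster | 235 | 235 − 30 = 205 | 205/235 = 87% |

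**3. Effect on the pooled estimate.** The protocol gives no figure for the size of any selection, so a range is shown. Let s be the difference in expected BDI between the two cluster arms that selection causes and that baseline adjustment does not remove. Weighting by patient numbers, bias = s × share.

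| Assumed s (BDI points) | Individual main trial | Cluster main trial |
|---|---|---|
| 1 | 0.15 | 0.87 |
| 2 | 0.31 | 1.74 |
| 3.5 | 0.54 | 3.05 |

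For s = 1 this is 0.15/3.5 = 4% or 0.87/3.5 = 25% of the target difference. If the analysis gives clustered patients less weight by the factor 1.45, the shares become (30/1.45)/(30/1.45 + 165) = 11% and (205/1.45)/(205/1.45 + 30) = 82%. The picture is the same.

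**4. What the section 22.2 check can see.** Take individually randomised sites as the reference and equal numbers in the two cluster arms:

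- Selection of size d in one cluster arm only: the cluster mean moves by (d + 0)/2 = d/2.
- Selection of +d/2 in one arm and −d/2 in the other: the cluster mean moves by (d/2 − d/2)/2 = 0, while the arms differ by d.

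**5. What a comparison by arm could see in the pilot.** With 30 v 30 cluster-allocated patients, SD 9 (taken as the baseline SD, an assumption) and design effect 1.45, SE = 9 × √(2 × 1.45/30) ≈ 2.8 BDI points. Power to detect a 3.5-point imbalance is about 24%, and for 1 point about 6%. With 205 v 205 in a cluster main trial, power for 3.5 points is about 90%.

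**The case against.** Three stronger readings are tempting, and the protocol does not support them.

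**That GPs are known to screen the list with the arm in hand.** The protocol does not say so. Section 11 describes the randomisation of practices, not its disclosure, and section 14 describes training in the trial design, not in the practice's allocation. A practice that delivers one arm will learn it from its first participant at the latest, but a first mailing list could be screened before then. What stands is that the order is not fixed and nothing is done to keep the arm from the practice.

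**That the section 22.2 check compares the wrong groups.** It is meant to compare recruitment approaches and levels of allocation, and for that its groups are right. It is not wholly blind to selection by arm either, since one-sided selection shows at half size. A baseline table by arm may also be in the statistical analysis plan, which is not at hand, so it cannot be called absent from the trial. What stands is narrower: the check that the protocol itself sets out for bias from recruitment, before the main trial, does not name this contrast. The order of list screening is a recruitment procedure that an analysis plan would not normally settle.

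**That the result will be biased by almost one BDI point.** That figure needs both the assumed 1-point shift and the switch to clusters, whereas the stated aim is individual randomisation.

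The existing safeguards also count. The list comes from coded searches, and GPs can only remove names. Letters are standard, and patients opt in themselves. Researchers, not GPs, check eligibility, and the entry BDI is completed by the patient. Posters and forms are freely available in the waiting room, and the analysis adjusts for baseline score. GP removal also has an evident protective use. These lessen the risk, but they do not bring back patients who were never invited or balance what is not measured.

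**Conclusion.** The point holds in a limited form. In cluster-allocated practices there is an open route for selection to differ by arm, and no step in the protocol closes it. The planned check would show such selection only in part.

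The consequence is modest if the main trial is individually randomised and material if it switches to clusters: about 0.15 and 0.87 BDI points respectively, for a residual shift of 1 point, against a target of 3.5. These sizes rest on the assumed shift, an even split of the pilot cluster patients, and weighting by patient numbers. They show what is at stake and are not an estimate of actual bias. The switch is a branch that sections 11 and 24 explicitly keep open, so the procedure should be settled before that decision.

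**What to change.** **Sections 10.3 and 11.** Require each cluster-allocated practice to run the database search, complete the GP exclusions, log each with a reason, and lock the list before its allocation is disclosed. This matters most for the new practices if the main trial switches to clusters. It is feasible there because section 11 recruits them only after the pilot decision.

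**Section 22.2.** Add a descriptive comparison of intervention-cluster with control-cluster practices on number excluded, recruitment rate, recruitment route, baseline BDI and debt priority. This also monitors the flyer route, which locking the list does not cover. In the pilot it should be read descriptively and not made a decision rule, because about 24% power for a 3.5-point imbalance is too little to support one.

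**Cost.** Allocation is disclosed to practices slightly later, and there is one extra table. Sample size and analysis model do not change.

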10.4 Baseline assessment visit

The baseline visit will usually be held in the patient's home but otherwise will take place in a location convenient for the patient and researcher. At the start of this visit, patients will be asked to confirm that they continue to have worries about debt. The researcher will then obtain written consent to participate in the study (see below) - unless the participant has already given consent and had their eligibility to take part confirmed within the previous two weeks at their GP practice. Following consent, patients will complete the BDI to check eligibility to take part in the study and as baseline assessment data. Patients who are not eligible to take part (i.e. scoring <14) will be advised as to why they are not eligible to take part, thanked for their time and willingness to participate and given the same study-specific debt advice leaflet and RCPsych leaflet as those given to people participating in the study. Ineligible patients will have no further involvement in the study.

Participants who indicate that they are actively suicidal at the baseline visit will be encouraged to contact the study GP promptly, before any further participation in the study. The researcher will explain that the study GP or the on-call GP will be informed of the researcher's concerns about the participant's welfare and current risk – with or without the participant's permission. The visit will be brought to a close and the researcher will explain to the participant that he/she may continue with the study, if desired, once the current risk has been discussed with a GP. If so, the RA will explain that he/she will contact the GP in approximately two weeks to check if it would be appropriate to re-contact the participant. The purpose of the RA re-contacting the GP is to ensure that further participation in the study has been assessed as appropriate by a clinical expert.

